4.1.2 Exclusion Criteria

Subjects meeting any of the following criteria will be excluded from the study:

1. History of being vaccinated in the past 5 years against pertussis (subject recall).
2. Any significant past reaction to any component of Boostrix (at the discretion of the investigator).

3. Subject reported diagnosis of pertussis in the past 10 years (must be laboratory confirmed or physician diagnosed from medical records).
4. Vital signs by toxicity scoring >1 (may be repeated once during the screening period to allow for inclusion and the most recent measurement taken at baseline).
5. Chronic illness being treated actively and with evidence of recent intervention for worsening or fluctuating symptoms (at the discretion of the investigator).
6. The subject has a history of active cancer (malignancy) in the last 10 years (exception is subjects with adequately treated non-melanomatous skin carcinoma, who may participate in the study).
7. Current use of any smoking products and unwillingness to refrain from the use of any smoking products from screening through 28 days after the boosting vaccination.
8. Use of narcotic drugs, evidenced by urine toxicology screen or a history of drug/alcohol abuse within the past 2 years.
9. Has donated blood or suffered from blood loss of more than 450 mL (1 unit of blood) within 60 days prior to screening, or donated plasma within 14 days prior to screening.
10. Receipt of immunoglobulin, blood-derived products, systemic corticosteroids, or other immunosuppressant drugs within 90 days prior to Day 1.
11. Asthma*, obstructive nasal canal, recurrent or acute sinusitis or other chronic respiratory problems inclusive of the diagnosis of any significant pulmonary disease.
*Asthma as diagnosed with spirometry showing reversibility of disease and must meet at least Step 1 classification with current prescription/use of medications to control symptoms (EPR-3 2007).
12. History of nasal surgery or Bell's palsy.
13. Use of repeated nasal sprays, Neti pot, or nasal washing within the past 1 month (more than 2 times per week). Subjects must agree to refrain from use of any of these modalities through Day 113.

14. A temporary exclusion to vaccinate if acute respiratory tract infection or rhinorrhea or temperature $>100.4^{\circ}\text{F}$ (no symptoms for 3 days prior to Vaccination Day). Subjects may be vaccinated if they stay within the vaccination window (screening [30 days] or at the time of the booster [10 days]).

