6.3.5.4 Assessing and Documenting Adverse Events

Safety will be assessed by the frequency and severity of:

1. Serious AEs occurring from the time of vaccination through the end of the study.
2. Solicited reactogenicity – reactogenicity events occurring from the time of each study vaccination through 7 days after each study vaccination:
 - a. Nasal/respiratory reactions including runny nose, stuffy nose/congestion, nasal pain/irritation, epistaxis, sneezing, sinus pressure/pain, sore/irritated throat, cough, and shortness of breath/wheezing.
 - b. Systemic reactions including fever, fatigue, malaise, myalgia, arthralgia, headache, and rash/hypersensitivity.
 - c. Local reactions – pain, tenderness, erythema/redness, induration/swelling
3. Unsolicited AEs – all AEs regardless of causality, will be collected for 28 days after each vaccination. Adverse events related to vaccination will be collected through Day 113. Between screening (signing of ICF) and Day 1, AEs will be collected if classifies as serious or if related to study procedure or study involvement. Any AE that results in vaccination delay (eg, temporary exclusions due to acute illness or fever, or investigator determined medical condition) during screening or during study conduct will also be recorded as an AE. Any newly identified potential AE of special interest will be followed through Day 254.
4. Any scheduled safety laboratory value that results in a Grade 3 toxicity score in the safety cohort will be recorded as an AE. Recording will be appropriate for either the

variable itself (eg, elevated creatine) or the condition which is diagnosed (eg, dehydration or chronic renal insufficiency).

At every study visit, subjects will be asked a standard nonleading question to elicit any medically related changes in their well-being. They will also be asked if they have been hospitalized, had any accidents, used any new medications, or changed concomitant medication regimens (both prescription and over-the-counter medications).

In addition to subject observations, AEs identified from any study data (eg, laboratory values, physical examination findings) or identified from review of other documents (eg, subject diaries) that are relevant to subject safety will be documented on the AE page in the eCRF.

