4.4. Analysis Periods

Safety data will be summarized by analysis period as outlined below.

- Prime Period:

This period starts on the day of primary vaccination (prime dose) at Day 1/Visit 1 and ends on either: (1) the day prior to second vaccination (boost dose) on Day 85/Visit 5 for those who received a boosting dose; or (2) the day of early termination visit if the subject discontinued before Day 85/Visit 5; or (3) the last known study day if the subject is lost to follow-up prior to Day 85/Visit 5.

- Boost Period:

This period starts on the day of boosting vaccination (boost dose) at Day 85/Visit 5 and ends on either: 1) the day of Day 113/Visit 8; or 2) the day of the discontinuation visit if the subject discontinued prior to or at Day 113/Visit 8; or 3) the last known study day if the subject lost to follow-up prior to Day 113/Visit 8.

- Long term safety follow-up:

This period starts at the next day after Day 113/Visit 8 or discontinuation visit and stops at the last follow-up visit or the last assessment date.

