9.2. Unsolicited Adverse Events

Unsolicited Adverse events will be coded according to Medical Dictionary for Regulatory Activities (MedDRA) version 22.0 or above. Unless otherwise specified, unsolicited AEs will be summarized by System Organ Class (SOC) and Preferred Term (PT), with SOCs sorted in the alphabetical order and PTs within each SOC in descending order of subject incidence. Partial missing unsolicited adverse event start dates will be imputed based on Appendix 13.4.

TEAE is defined as an AE that starts or an existing AE that worsens on or after the date of prime vaccination. AE will be summarized by period, including Day 1 to Day 84, Day 85 to Day 113, and Day 114 to End of Study (EOS). From Day 1 to Day 29, all AE regardless causality will be recorded and summarized. From Day 30 to Day 84, all AE related to vaccination and SAE will be recorded and summarized. From Day 85 to Day 113, all AE regardless causality will be recorded and summarized. From Day 114 through end of study (EOS), all SAE will be recorded and summarized.

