13.1. Schedule of Study Procedures

Table 13-1

Procedure	Screening	Treatment Period									
		0	1	2	3	4	5	6	7	8	9
Study visit											
Days relative to most recent vaccination	-30 to 0	1	8	29	78	85/1	8	12	29	85	169
Days relative to first vaccination^b	-30 to 0	1	8	29	78	85	92	96	113	169	254
Window allowance	30	0	+3	+7	-7	+10	+2	+/-2	+7	-7	±15
Informed consent	X										
Inclusion/exclusion criteria	X	X ^c				X ^c					
Demographic and baseline data ^d	X										
Medical history ^e	X	X ^c				X ^c					
Medication ^f	X	X	X	X	X	X	X	X	X	X ^g	X ^g
Serology ^h	X										
Urine drug screen	X										
Physical examination ⁱ	X	X ^j	X	X		X ^j	X	X	X		
Vital sign measurements	X	X ^k	X	X		X ^k	X	X	X		
Safety laboratory tests for enrollment ^l	X										
Safety laboratory tests for safety cohort ^m	X		X			X ⁿ	X				
Urine pregnancy test (female subjects of childbearing potential)	X	X ⁿ				X ⁿ					
Randomization		X									
Vaccination ^o		X				X					
Subject diary dispensing ^p		X				X					
Subject diary reviewed ^q			X				X				
Reactogenicity - post vaccination		X ^r	X ^s			X ^r	X ^s				
Immunogenicity laboratory tests for serumpertussis IgG and IgA ELISA		X ⁿ		X		X ⁿ			X	X	X
Mucosal pertussis nasal antibody testing (S-IgA ELISA) – nasal absorption device ^t	X ^u			X	X				X	X	X
Nasal collection for B. pertussis colonization					X ^v		X	X	X ^v		X ^w
PBMC for cellular immunity (subset of no more than 60 subjects)		X	X				X				

Collection of serious adverse events and adverse events of special interest only x										X	X
Adverse events xy		X	X	X	X	X	X	X	X		
End-of-study form completion											X

Abbreviations: ELISA, enzyme-linked immunosorbent assay; Ig, immunoglobulin; PBMC, peripheral blood mononuclear cell; S-IgA, secretory immunoglobulin A.

- a End-of-study Visit.
- b Days relative to vaccination are only estimates as the window allowance is not inclusive. Should a study pause occur than vis its/windows will be adjusted to allow for subjects to continue without protocol deviation. Visit schedule following the boosting vaccination is calculated relative to the day the boosting vaccination was received.
- c Inclusion/exclusion criteria and medical history will be reviewed and updated on Day 1 and Day 85 with specific vaccination exclusions applied.
- d Including date of birth (day, month, and year), sex, race, ethnicity, weight, height, and body mass index(derived).

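### SAP 9.2 cuts adverse events at fixed study days, SAP 4.4 cuts them at the actual boost, and the SAP does not say which rule governs the tables

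*SAP*

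**What the plan says.** **Fixed days.** SAP 9.2 states that "AE will be summarized by period, including Day 1 to Day 84, Day 85 to Day 113, and Day 114 to End of Study", and then "From Day 114 through end of study (EOS), all SAE will be recorded and summarized". SAP 9.2.7 (events leading to study discontinuation) repeats the three day ranges. SAP 9.2.6 (events leading to withholding of the second vaccination) covers Day 1 to 84 only. SAP 9.2.8 (deaths) splits at Day 113/114 only.

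**Actual boost.** SAP 4.4 sets the analysis periods for safety data. The prime period ends the day before the second vaccination. Of the boost period it says: "This period starts on the day of boosting vaccination (boost dose) at Day 85/Visit 5 and ends on either" Visit 8 or an earlier discontinuation or last known day. SAP 9.2.1 asks for the overview of treatment-emergent events by the prime and boost analysis periods, which are the terms of 4.4.

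**When the boost is given.** The window row of the SAP 13.1 schedule reads "Window allowance 30 0 +3 +7 -7 +10", where the last entry belongs to Visit 5, the boost. Protocol 4.1.2, exclusion 14, agrees: "at the time of the booster [10 days". The design text (Protocol 3.1, SAP 3.1) gives +7 days. A study pause can move the boost further, with no stated limit. Footnote b of the schedule adds: "Visit schedule following the boosting vaccination is calculated relative to the day the boosting vaccination was received".

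**What is collected.** Protocol 6.3.5.4 says that "all AEs regardless of causality, will be collected for 28 days after each vaccination". Protocol 7.7.2 pools A+C and B+D for adverse events through 28 days after the boost. SAP 11 declares no departure from the protocol's analyses.

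**The concern.** If every boost fell on Day 85, the two rules would coincide. The window allows only late boosts, so each off-nominal boost inside it pushes the two rules apart in the same direction. A programmer who follows 9.2 and one who follows 4.4 would place some events of a late-boosted subject in different periods.

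Unsolicited adverse events in the 28 days after each vaccination are a secondary safety endpoint for a live intranasal vaccine. At stake is whether the boost tables hold what happened after the boost and nothing that happened before it. The overview (9.2.1) and the detailed tables (9.2.6, 9.2.7) could also disagree within one report.

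**Working it through.** **Inputs.** Fixed periods: Days 1–84, 85–113, 114 to end of study (SAP 9.2). Collection: 28 days after each vaccination (Protocol 6.3.5.4). Boost window: Day 85 +10 (schedule, exclusion 14) or +7 (design text). Visit 8: 28 days after the actual boost, window +7 (schedule and footnote b).

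**The plan's own figures.** 1 + 28 = 29 and 85 + 28 = 113. Both match the limits in SAP 9.2, so the fixed days are right for a boost exactly on Day 85.

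**Boost on day b = 85 + k, with 9.2 read literally.**

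- End of the 28 post-boost days: b + 28 = 113 + k
- Pre-boost days labelled boost: b − 85 = k
- Post-boost days beyond Day 113: (b + 28) − 113 = k, a share of k/28

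| Boost day | 28 days end on | Pre-boost days labelled boost | Post-boost days after Day 113 | Post-boost days kept | Visit 8, ending the 4.4 boost period |
|---|---|---|---|---|---|
| 85 | 113 | 0 | 0 of 28 | 28 | Day 113–120 |
| 92 (+7) | 120 | 7 | 7 of 28 (25.0%) | 21 | Day 120–127 |
| 95 (+10) | 123 | 10 | 10 of 28 (35.7%) | 18 | Day 123–130 |
| 99 (assumed, after a pause) | 127 | 14 | 14 of 28 (50.0%) | 14 | Day 127–134 |

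Under SAP 4.4 both error columns are zero for every boost day, provided Visit 8 is held in its window.

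**One subject under the two rules.** A non-serious illness starts on Day 86 and delays the boost to Day 95. Protocol 6.3.5.4 requires an event that delays vaccination to be recorded. Under 4.4 it is a prime-period event; under 9.2 it is a boost-period event. A non-serious event on Day 118, 23 days after that boost, is a boost-period event under 4.4. Under 9.2 it falls where only serious events are summarized.

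**Withheld boost.** If the Day 86 illness leads to the boost being withheld, the Day 1–84 limit keeps it out of the 9.2.6 table. SAP 4.4 does not help here. It ends the prime period only for subjects who are boosted, who discontinue before Visit 5 or who are lost before Visit 5. Protocol 4.2.2 expects unboosted subjects to stay in follow-up.

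**The case against.** The best defence is that the day numbers in 9.2 are nominal labels. SAP 4.4 says how safety data are divided, and 9.2.1 uses its terms. Footnote b calls the days estimates and counts post-boost visits from the actual boost. The SAP elsewhere uses Day 85 as a name for the second vaccination. On that reading Day 113 means boost + 28 and nothing is misplaced.

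This reading is possible but not stated. Where 4.4 means a visit it pairs the day with a visit number; 9.2 does not. Days 30, 84 and 114, which 9.2 uses as limits, are not visits in the schedule. No sentence gives 4.4 precedence.

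Three parts of the defence do stand.

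- A reader might infer that post-boost events go uncollected. The protocol still requires 28 days of collection after each vaccination, and SAP 4 lists all collected data. The effect is on tabulation, although 9.2 loosely says recorded as well as summarized.
- A reader might infer that the comparison of A+C with B+D is materially diluted by pre-boost events. The documents give no basis for a size. Once 28 days have passed since the prime dose, the protocol collects only vaccination-related events, serious events and events that delay vaccination, so few events can be misplaced in this way. The tables are descriptive and no hypothesis is tested.
- SAP 9.2.8 has no prime/boost split, and deaths are serious events summarized in every period. No death drops out; only the Day 113/114 boundary needs aligning.

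**Conclusion.** The SAP holds two conflicting period rules for adverse events and does not rank them. The literal reading of 9.2 also conflicts with the protocol's 28-day window after each vaccination. That is a defect of the text as written; it does not show that the analysis will misassign events.

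Under the literal reading, 7 of 28 post-boost days fall outside the boost tables for a subject boosted at +7, and 10 of 28 at +10. The same number of pre-boost days is taken in. These are per-subject figures at the edge of the window, and 10 is the ceiling only inside the schedule's window; a pause could exceed it. No distribution of boost dates is given, so no table-level effect can be stated. The gap in 9.2.6 likewise depends on the literal reading, while the missing prime-period end for unboosted subjects does not.

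**What to change.** - In SAP 9.2, 9.2.6 and 9.2.7, replace the fixed days with the 4.4 periods anchored on the actual boost date, and move the Day 113/114 cut in 9.2.8 to the same boundary.
- State that all adverse events are recorded and summarized for 28 days after the actual boost.
- Choose one end of the boost period, Visit 8 or boost + 28 days, and use it in both 4.4 and 9.2. Visit 8 can fall 28 to 35 days after the boost, so writing boost + 28 into 9.2 alone would create a new mismatch.
- Add to 4.4 a prime-period end for subjects never boosted who stay in follow-up, for example the nominal Visit 5 date.
- Let 9.2.6 include any event leading to withholding of the boost, whatever its study day.
- Reconcile the +7 and +10 boost windows between the design text and the schedule with exclusion 14.

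The cost is SAP wording and some programming. Vaccination dates are already recorded in the eCRF (SAP 7.2.1), so no new data are needed.

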2.5.4 Secondary Safety Endpoints

- Unsolicited AEs (eg, treatment-emergent AEs, SAEs, and suspected unexpected serious adverse reactions [SUSARs]) collected for 28 days following each vaccination by Medical Dictionary for Regulatory Activities (MedDRA) classification and severity score.
- Unsolicited AEs related to vaccination through Day 113 by MedDRA classification and severity score.
- Serious AEs through 6 months following the last vaccination (or until resolved or stable) by MedDRA classification, relatedness, and severity score.
- Vital sign measurements with severity scoring immediately following vaccination.

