9.2.1. Incidence of Adverse Events

An overview summary of the following TEAE categories for the prime and boost analysis period will be provided separately:

- Any TEAE

- Any TEAE related to vaccination
- Any severe TEAE
- Any serious TEAE
- Any serious TEAE related to vaccination
- Any TEAE Leading to Withholding of Day 85 Vaccination
- Any TEAE leading to study discontinuation
- Any TEAE leading to death

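### The prime-period adverse event overview (Day 1-84) pools 29 all-cause days with 55 related-or-serious-only days, so its any-TEAE row is not the protocol's 28-day endpoint and does not match the boost overview

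*SAP*

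**What the plan says.** SAP 9.2 sets the reporting blocks: "AE will be summarized by period, including Day 1 to Day 84, Day 85 to Day 113", followed by Day 114 to end of study. The same paragraph sets three collection rules within the first two blocks:

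- Early prime: "From Day 1 to Day 29, all AE regardless causality will be recorded and summarized".
- Late prime: "From Day 30 to Day 84, all AE related to vaccination and SAE will be recorded and summarized".
- Boost: "From Day 85 to Day 113, all AE regardless causality will be recorded and summarized".

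SAP 4.4 confirms that the prime period is one block. Its start is defined as "This period starts on the day of primary vaccination (prime dose) at Day 1/Visit 1", and its end, for boosted subjects, as "the day prior to second vaccination (boost dose) on Day 85/Visit 5 for those who received a boosting dose". SAP 9.2.1 builds its tables on these blocks: "An overview summary of the following TEAE categories for the prime and boost analysis period will be provided separately". The rows include any, related, severe and serious TEAEs. It specifies no 28-day table for the prime dose, no exposure adjustment and no footnote.

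Protocol 2.5.4 has two separate endpoints where the prime block has one. Unsolicited AEs are "collected for 28 days following each vaccination", and vaccination-related AEs through Day 113 are listed in their own bullet. SAP 3.2.2.4 repeats both. Protocol 6.3.5.4 adds that AEs which delay a vaccination are also recorded. SAP section 11 states that nothing in the planned analyses was changed from the protocol.

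**The concern.** The collection rule changes inside the prime period, but the table does not. After Day 29, with the exception of AEs that delay vaccination, an event can enter the prime any-TEAE row only if it is judged related or is serious. The row is therefore neither a 28-day all-cause proportion nor an 84-day one. The same filter can only raise the related share of prime TEAEs.

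Readers have reason to set the two overviews side by side. The secondary safety objective concerns related AEs after one or two doses, and the rationale includes the safety of BPZE1 as a booster after Boostrix. The first BPZE1 dose falls in the prime table for Arms A and B and in the boost table for Arm C. Related and serious events are counted for longer in the first table than in the second. At stake is whether the reported secondary safety proportions match the stated endpoint and can be read across doses.

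**Working it through.** **Inputs.** The day labels come from SAP 9.2, the period limits from SAP 4.4 and the 28-day endpoint from Protocol 2.5.4.

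**1. The plan's own figure.** Days after vaccination = last day − vaccination day. Prime: 29 − 1 = 28. Boost: 113 − 85 = 28. The SAP's all-cause windows reproduce the protocol's 28 days after each dose.

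**2. Calendar days (last − first + 1)**

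| Window | Collection | Days |
|---|---|---|
| Day 1-29 | all AEs | 29 |
| Day 30-84 | related AEs and SAEs | 55 |
| Day 1-84 | mixed | 84 |
| Day 85-113 | all AEs | 29 |

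All-cause collection covers 29/84 = 34.5% of the prime period and 29/29 = 100% of the boost period. A later boost lengthens the prime block. With the boost on Day 92 (+7 days, SAP 3.1 text) or Day 95 (+10 days, schedule table), the restricted part is 62 or 65 days. The documents give both windows, and these need reconciling.

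**3. Time at risk by type of event**

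| Event | Prime | Boost | Ratio |
|---|---|---|---|
| Nonserious, unrelated | 29 | 29 | 1.0 |
| Related or serious | 84 | 29 | 84/29 = 2.90 |

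The any-TEAE row is the union of these. The severe row is also mixed: severe events that are related or serious count for 84 days, and other severe events for 29.

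**4. Illustration of size.** The documents give no AE rates, so these inputs are assumptions: a constant daily hazard λ, identical after both doses, 30% of subjects with any AE in 29 days, and a share s of the hazard that is related or serious.

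- λ = −ln(1 − 0.30)/29 = 0.0123 per day
- Any TEAE: boost = 1 − exp(−29λ) = 30%; prime = 1 − exp(−λ(29 + 55s))
- Related or serious: boost = 1 − exp(−29λs); prime = 1 − exp(−84λs)

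| s | Any TEAE, prime | Any TEAE, boost | Related or serious, prime | Related or serious, boost |
|---|---|---|---|---|
| 0% | 30.0% | 30.0% | 0% | 0% |
| 5% | 32.3% | 30.0% | 5.0% | 1.8% |
| 10% | 34.6% | 30.0% | 9.8% | 3.5% |
| 20% | 38.9% | 30.0% | 18.7% | 6.9% |
| 30% | 42.9% | 30.0% | 26.7% | 10.1% |

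For s from 5% to 30%, a 20% base gives prime any-TEAE of 21.7% to 29.5%, and a 40% base gives 42.8% to 55.1%. An assumed SAE proportion of 1% in the boost period becomes 1 − 0.99^(84/29) = 2.9% in the prime period. Related events that cluster soon after vaccination would shrink all these gaps.

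**5. After the change.** With both tables cut at 28 days after the dose, the windows are 29 and 29 calendar days, and equal hazards give equal expected proportions.

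**The case against.** The strongest reply is that no planned comparison is affected. The study is descriptive, and safety is shown by arm within each period: A+B and C+D after the prime, A+C and B+D after the boost. All arms in a period share the same collection rules. Protocol 7.7.2 already ties the pooled post-boost AE assessment to 28 days. This stands.

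Second, a reader might infer that a boost as reactogenic as the prime, or more so, could look better tolerated. The documents do not support that for reactogenicity. It is the primary safety endpoint and is solicited for 7 days after each dose, with the same nasal/respiratory and systemic windows. Local reactions are collected only after Day 1, by design.

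Third, longer follow-up of related events after the prime is the protocol's own design, because related AEs through Day 113 is a stated endpoint. That justifies collecting and reporting those events. It does not justify adding them to an all-cause row.

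Fourth, SAP 9.2 says that Day 1-29 events and Day 30-84 events are each summarized, which could mean separate sub-window tables. If so, SAP 9.2.1 does not carry it through: its rows are specified by whole analysis period. SAP 9.2.6 and 9.2.7 also use Day 1-84.

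**Conclusion.** The prime overview as specified does not report the protocol's endpoint of unsolicited AEs for 28 days after vaccination, and the prime and boost overviews do not cover the same collection. The mismatch lies in related and serious events, counted over 84 days against 29, and it carries into the any-TEAE and severe-TEAE rows.

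Two stronger readings go too far. A reader might infer that the reported rates must differ by construction. Only the observation windows do: nonserious unrelated AEs have equal windows, and if no qualifying event starts on Day 30-84 there is no excess. A reader might also infer that a first BPZE1 dose in Arms A and B has 112 days of related-event follow-up in the table against 28 in Arm C. Events from Day 85 fall in the boost block, and Arm A has by then had a second BPZE1 dose. The prime table itself covers 84 days.

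The range of about 32-43% against 30% rests wholly on the assumed constant and equal hazards, the 30% base and the 5-30% share. It shows the direction and possible scale and is not a forecast. This is a defect in how a secondary safety endpoint is reported, and it biases no planned contrast.

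**What to change.** In SAP 9.2.1 to 9.2.3:

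1. Tabulate any, related, severe and serious TEAEs from the date of each dose through 28 days after it, anchored on the actual dose date. Use these tables for the 28-day endpoint and for any reading across doses, including the first BPZE1 dose in A+B beside that in C. Equal windows put those two on the same observation time; they do not make the contrast a randomized one.
2. Show related AEs and SAEs from Day 30 to the day before the boost in a separate, labelled table that is not added to the any-TEAE row. State there that AEs which delay vaccination are also recorded, and where they are counted.
3. Keep related AEs through Day 113 as its own summary, as the protocol lists it.

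The cost is SAP wording and table shells. The events and their dates are already collected, so no visit, form or sample size changes.
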